5.4. Key Secondary Endpoints

The key secondary efficacy outcomes (objectively confirmed – CEC Adjudicated) are:

- symptomatic VTE events (symptomatic lower extremity proximal DVT, symptomatic lower extremity distal DVT, symptomatic upper extremity DVT and symptomatic non-fatal PE) or VTE-related deaths
- All-cause mortality

5.4.1. Definition

The key secondary efficacy endpoints defined based on the key secondary efficacy outcomes above are as follows:

- Time to first occurrence of objectively confirmed symptomatic VTE events (symptomatic lower extremity proximal DVT, symptomatic lower extremity distal DVT, symptomatic upper extremity DVT, or symptomatic non-fatal PE) and VTE-related deaths
- Time to all-cause mortality

5.4.2. Analysis Methods

Analysis of the key secondary efficacy endpoints will follow the same approach as in the analysis of the primary efficacy composite endpoint analysis. The analysis will be based on the ‘Up-to-Day 180’ observation period for ITT population with censoring as defined above (Section 2.6). Each of the key secondary endpoints will be tested using a log-rank test, stratified by tumor type.

For each of these two key secondary endpoint analyses, a Cox proportional hazard model with treatment and stratification factor as covariates will be fitted. A point estimate along with 2-sided 95% CI for the treatment effect of RRR (RRR=100 x [1-HR] %) will be provided.

The cumulative event rate derived from Kaplan-Meier estimate will also be displayed graphically to evaluate the timing of event occurrence and the consistency of the treatment effect over time.

Summary of Key Secondary Efficacy Endpoints Analysis Methods			
Endpoint	Observation Period	Analysis Population	Method
Key Secondary Endpoints 1. Composite of symptomatic VTE events or VTE-related death 2. All-cause mortality (CEC Adjudicated Events)	Up-to-Day 180	ITT	Kaplan-Meier Estimates (Cumulative event rates and stratified log-rank test) Cox-model (HR, 95% CI)

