2.6.1. Up-to-Day-180 Observation Period

This observation period includes data from randomization to Up-to-Day 180 end date (defined in Section 2.5).

Event: All efficacy events (with respect to deaths, *VTE-related deaths are counted as events for primary efficacy endpoint. For the secondary efficacy endpoints, all-cause deaths are counted as events*) that occurred from randomization through the Up-to-Day 180 end date (Section 2.5) will be included in the analysis of this observation period.

- Event time - The time to event is defined as the time from randomization to the time of the first event during this observation period.

Censoring: Subjects who did not experience an event during this observation period will be censored at the last day of their complete assessment for study outcomes.

Subjects who died during this observation period will be censored as of their death date for endpoint analyses not related to death.

- Censoring time - The time to censoring is defined as the time from randomization to the minimum of (last day of their complete assessment for study outcomes during the double-blind period [double-blind completion/withdrawal], death date [non VTE-related deaths for primary efficacy composite endpoint]).

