 - a. If subject experiences an efficacy composite endpoint event (primary or secondary, including VTE-related deaths) after withdrawing from the study and the time to the occurrence of the event is prior to Day 180, then this event and corresponding time to the occurrence of the event will be included in the analysis of primary efficacy composite endpoint. If subject dies (all causes other than VTE-related) after withdrawing from the study and reported on Day 210 but event time is prior to Day 180, then this event and corresponding time to death will be included in the all-cause mortality endpoint analysis
 - b. If a subject does not experience any efficacy composite endpoint event (primary or secondary) in the study, then this subject will be censored. The time to censoring is defined as the time from randomization to the minimum of (last day of their complete assessment for study outcomes during the double-blind period/Day 180 [double-blind withdrawal date for those who withdrew], or death date [censored at death date for analysis not related to the specific death endpoint]).

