5.3. Competing Risk Analysis

Competing risks arise when subjects are at risk of experiencing more than one cause of failure (event) and failure due to other causes precludes observing the main cause of interest (i.e. censored for primary efficacy composite endpoint).

The primary efficacy composite endpoint is defined as a composite of objectively confirmed symptomatic lower extremity proximal DVT, asymptomatic lower extremity proximal DVT, symptomatic lower extremity distal DVT, symptomatic upper extremity DVT, symptomatic non-fatal PE, incidental PE or VTE-related death (adjudicated by CEC). For this type of outcome (the primary endpoint), a death due to causes other than VTE-related is a competing risk event and, as such, a patient is no longer at risk of having any of the events of interest.

To account for competing risks (deaths from causes other than venous thromboembolism related; VTE-related deaths are included in the primary efficacy composite endpoint) in the primary efficacy analysis, a cumulative incidence approach will be followed with the use of Gray's (1988)⁹ two-sample test (two-sided alpha level, 0.05). Hazard ratios and 95% confidence intervals will be calculated with the use of the Fine and Gray (1999)¹⁰ regression model (with treatment group as a factor). Cumulative incidence functions (defined as the cumulative probability of failure from a specific cause over time) will be estimated separately for the two study groups. These analyses will be based on the '**Up-to-Day 180**' observation period for the ITT population with censoring as defined above in Section 2.6.

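### The first key secondary endpoint has only Kaplan-Meier cumulative rates with non-VTE deaths censored, which overstates each arm's absolute risk; 5.3 gives the primary composite a cumulative incidence function but not this endpoint

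*SAP*

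**What the plan says.** SAP 5.4.1 defines the first key secondary endpoint as time to symptomatic VTE or VTE-related death. Under 5.5 it is second in the testing hierarchy, after the primary composite.

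For its analysis, 5.4.2 states "Analysis of the key secondary efficacy endpoints will follow the same approach as in the analysis of the primary efficacy composite endpoint analysis". The methods listed are a stratified log-rank test, a Cox model and Kaplan-Meier curves: "The cumulative event rate derived from Kaplan-Meier estimate will also be displayed graphically to evaluate the timing of event occurrence" and, as the sentence goes on, the consistency of the effect over time. The effect measure is relative: "A point estimate along with 2-sided 95% CI for the treatment effect of RRR (RRR=100 x [1-HR] %) will be provided". The summary table in 5.4.2 gives "Kaplan-Meier Estimates (Cumulative event rates and stratified log-rank test) Cox-model (HR, 95% CI" and nothing else. Section 5.6.2 names the key secondary endpoints again with the same three methods. It also covers composite endpoint #2 of 5.6.1, which is this endpoint under another label.

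On deaths, 2.6.1 says "Subjects who died during this observation period will be censored as of their death date for endpoint analyses not related to death", and 4.6 says "censored at death date for analysis not related to the specific death endpoint". Section 2.6.1 also contains a parenthetical remark that, for the secondary efficacy endpoints, deaths from any cause are events.

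Section 5.3 says of the primary composite that "a death due to causes other than VTE-related is a competing risk event and, as such, a patient is no longer at risk". It plans cumulative incidence functions, Gray's test and a Fine-Gray model for that composite. The primary summary table in 5.2.3 has a competing-risk row; the table in 5.4.2 has none.

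**The concern.** The two composites have the same structure: VTE components plus VTE-related death, with every other death ending follow-up. The reasoning in 5.3 applies to both, but only the primary composite receives an estimator that respects it.

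One minus Kaplan-Meier with competing deaths censored estimates the risk that would apply if nobody died of anything else. It is not the proportion of randomized subjects expected to have the event. The 5.4.2 table nevertheless labels it a cumulative event rate, and it is the only absolute quantity planned for this endpoint. Symptomatic events are the ones from which readers are likely to judge absolute benefit, and the population has cancer under systemic therapy, so non-VTE deaths within 180 days are to be expected. What is at stake is the absolute rates and anything derived from them, not the test.

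**Working it through.** **Inputs from the SAP**

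- Symptomatic VTE at 180 days: at least 12% (1.4). Section 1.4 cites Kaplan-Meier values of 17.7% (N=93) and 9.6% (N=221). Weighting by group size, (93 × 17.7 + 221 × 9.6) / 314 = 12.0%, which reproduces the figure. It is used here as the placebo Kaplan-Meier rate.
- Relative risk reduction: 58.6% (1.4), which is 8.5 / 14.5. It was planned for the primary composite; applying it to this endpoint is an assumption. It gives a rivaroxaban Kaplan-Meier rate of 12% × (1 − 0.586) = 4.97% and an implied difference of 7.03 points.

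**Input not in the SAP**

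- Non-VTE mortality by Day 180, q (net of VTE events): varied from 5% to 40%.

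**Formula.** With constant, independent cause-specific hazards over 180 days and Kaplan-Meier risk F, put l = −ln(1 − F) and m = −ln(1 − q). Then CIF = l / (l + m) × [1 − exp(−(l + m))]. Because m > 0 whenever non-VTE deaths occur, the CIF lies below F in each arm. Only the size of the gap depends on q.

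**Worked case, placebo, q = 20%.** l = 0.1278 and m = 0.2231, so l + m = 0.3510. Since exp(−0.3510) = 0.88 × 0.80 = 0.704, CIF = (0.1278 / 0.3510) × 0.296 = 10.78%.

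**Equal non-VTE mortality in both arms** (Kaplan-Meier 12.00% vs 4.97%, difference 7.03)

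| q | CIF placebo | CIF rivaroxaban | CIF difference | Relative overstatement, placebo rate |
|---|---|---|---|---|
| 5% | 11.70% | 4.84% | 6.86 | 2.5% |
| 10% | 11.40% | 4.72% | 6.68 | 5% |
| 20% | 10.78% | 4.46% | 6.32 | 11% |
| 30% | 10.13% | 4.18% | 5.95 | 18% |
| 40% | 9.45% | 3.90% | 5.55 | 27% |

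The risk ratio hardly moves: 0.414 by Kaplan-Meier and 0.413 to 0.414 by CIF.

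**Unequal non-VTE mortality** (same Kaplan-Meier rates)

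| q placebo | q rivaroxaban | CIF difference | Against 7.03 |
|---|---|---|---|
| 30% | 15% | 5.54 | Kaplan-Meier too high |
| 20% | 25% | 6.46 | Kaplan-Meier too high |
| 15% | 30% | 6.91 | Kaplan-Meier slightly too high |
| 5% | 30% | 7.52 | Kaplan-Meier too low |

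With a weaker effect a smaller imbalance reverses the sign. At a risk ratio of 0.8 (12.0% vs 9.6%, difference 2.40), mortality of 20% on placebo and 25% on rivaroxaban gives a CIF difference of 10.78 − 8.36 = 2.42.

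**Does the censoring premise hold?** The 5.4.1 definition, the 2.6.1 rule on deaths unrelated to the endpoint, and 4.6 all point to censoring. Read literally, the 2.6.1 remark on all-cause deaths would make every death an event and leave nothing to compete. That would turn the endpoint into symptomatic VTE or any death, which is neither the 5.4.1 definition nor the hypothesis in 5.5. Censoring is the better reading, but the text should not leave it open.

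**The case against.** Several points on the other side stand.

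- A reader might infer that the plan will report an inflated risk difference. It will not: the planned effect measure here is the hazard ratio expressed as a relative risk reduction, and no efficacy endpoint has a planned risk difference. A difference arises only if someone subtracts the two arm rates, and the tables above show that its error has no fixed sign.
- A reader might infer that the alpha-controlled test is compromised. It is not. The log-rank test and the Cox hazard ratio compare cause-specific hazards, for which censoring other deaths is the standard construction.
- A reader might infer that the SAP contradicts itself. That is too strong. The primary analysis in 5.2.2 also uses Kaplan-Meier with non-VTE deaths censored; the competing-risk work in 5.3 is an addition, and 5.3 does not call Kaplan-Meier invalid. Limiting the addition to the primary composite is a choice of scope.
- The 5.4.2 text presents the curves as a display of timing and consistency, not as estimates of the proportion affected. The table, however, lists cumulative event rates as output, and nothing warns against reading them as absolute risks.
- The same-approach sentence in 5.4.2 could be read as importing 5.3. But 5.3 confines itself to the primary efficacy analysis, and the 5.4.2 table omits it.

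The magnitude also rests on assumed mortality and on a relative reduction borrowed from another endpoint. At 5% non-VTE mortality the placebo excess is only 0.3 points.

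**Conclusion.** The point holds for the absolute rates. With non-VTE deaths censored, one minus Kaplan-Meier overstates the risk in each arm whenever such deaths occur, and the SAP offers no other absolute estimate for this endpoint although it plans one for its structural twin. On a 12% placebo rate the excess is about 0.6, 1.2 or 1.9 points at assumed non-VTE mortality of 10%, 20% or 30%. These sizes assume constant, independent hazards and a mortality the SAP does not state; the direction within each arm does not depend on the mortality figure. The implied difference between arms is overstated if mortality is similar in the arms, and otherwise may be too high or too low. Inference is untouched, so this is a cheap improvement in reporting and not a threat to the trial's conclusions.

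**What to change.** - In 5.3, extend the cumulative incidence function, with non-VTE death as the competing event, to the first key secondary endpoint and to composite endpoint #2, so that one endpoint is not handled in two ways.
- Add a matching row to the 5.4.2 summary table and a cross-reference in 5.6.2.
- State that any absolute risk quoted for this endpoint comes from that function.
- Keep the Kaplan-Meier curves, the stratified log-rank test and the Cox hazard ratio as planned. The cumulative incidence function then stands beside Kaplan-Meier, as it does for the primary composite, and the two composites can be compared on either scale. All-cause mortality needs no change, since it has no competing event.
- In the same edit, reconcile the 2.6.1 remark on all-cause deaths with 5.4.1, for example by limiting it to the endpoints that include all-cause mortality.

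The cost is a few lines of text and one more run of code already needed for 5.3. The only downside is that the absolute rates quoted will be slightly lower.

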5.5. Adjustment for Multiplicity

Superiority of rivaroxaban over placebo on the primary efficacy composite endpoint will be first established. If this is established, then a sequential approach using a closed testing hierarchical procedure (to control the family-wise type I error rate at alpha at 5%, 2-sided) will be used to test the following two secondary hypotheses:

- symptomatic VTE events + VTE-related deaths
- all-cause mortality

Overall Hierarchy of Testing Multiple Hypothesis	
Primary Efficacy Composite Endpoint (ITT/Up-to-Day 180)	
• Time to first occurrence of symptomatic lower extremity proximal DVT, asymptomatic lower extremity proximal DVT, symptomatic lower extremity distal DVT, symptomatic upper extremity DVT, symptomatic non-fatal PE, incidental PE or VTE-related death	$\alpha=0.05$
↓	
Secondary Efficacy Endpoints (ITT/Up-to-Day 180)	
• Time to first occurrence of symptomatic VTE events and VTE-related death	$\alpha=0.05$
↓	
• All-cause mortality	$\alpha=0.05$

5.6. Additional Secondary Efficacy Variable(s)

Additional secondary outcomes (objectively confirmed – CEC Adjudicated) are:

- Individual components of the primary efficacy composite variable
- Confirmed fatal/non-fatal arterial thrombosis event (ATE) (e.g. MI and stroke) events (these will include the following events: occurrence of a stroke, MI or any arterial thrombosis event)
- Confirmed fatal/non-fatal visceral VTE events
- Composite of symptomatic lower extremity proximal DVT, asymptomatic lower extremity proximal DVT, symptomatic lower extremity distal DVT, symptomatic upper extremity DVT, symptomatic non-fatal PE, incidental PE and all-cause mortality
- Composite of symptomatic lower extremity proximal DVT, symptomatic lower extremity distal DVT, symptomatic upper extremity DVT, symptomatic non-fatal PE and VTE-related deaths
- Composite of events in the primary efficacy composite endpoint, fatal/non-fatal ATE, visceral VTE
- Composite of symptomatic lower extremity proximal DVT, symptomatic lower extremity distal DVT, symptomatic upper extremity DVT, symptomatic non-fatal PE and VTE-related deaths and major bleeding events

5.6.1. Definition

Secondary efficacy endpoints defined based on the other secondary outcomes above are as follows:

- Individual components of the primary efficacy composite variable
 - Time to first occurrence of symptomatic lower extremity proximal DVT
 - Time to first occurrence of asymptomatic lower extremity proximal DVT
 - Time to first occurrence of symptomatic lower extremity distal DVT
 - Time to first occurrence of symptomatic upper extremity DVT
 - Time to first occurrence of symptomatic non-fatal PE
 - Time to first occurrence of incidental PE
 - Time to VTE-related death

In addition to the analysis of the individual components, concordance between the investigator reported events and the CEC adjudicated events will also be presented.

- Time to first occurrence of fatal/non-fatal ATE (a composite of occurrence of MI, stroke [ischemic infarction with or without hemorrhagic conversion or primary hemorrhagic events – intraparenchymal hemorrhage, subdural hematoma or epidural hematoma] or any other ATE recorded on eCRF) event.
- Time to first occurrence of fatal/non-fatal visceral VTE event (include only visceral (venous) events recorded on the eCRF).
- Composite endpoint #1: Time to first occurrence of the composite endpoint of symptomatic lower extremity proximal DVT, asymptomatic lower extremity proximal DVT, symptomatic lower extremity distal DVT, symptomatic upper extremity DVT, symptomatic non-fatal PE, incidental PE and all-cause mortality (*composite: primary efficacy composite endpoint event components but including all-cause mortality*).
- Composite endpoint #2: Time to first occurrence of the composite of symptomatic lower extremity proximal DVT, symptomatic lower extremity distal DVT, symptomatic upper extremity DVT, symptomatic non-fatal PE and VTE-related deaths (*composite: symptomatic events only and VTE-related deaths*).
- Composite endpoint #3: Time to first occurrence of the primary efficacy composite endpoint (symptomatic lower extremity proximal DVT, asymptomatic lower extremity proximal DVT, symptomatic lower extremity distal DVT, symptomatic upper extremity DVT, symptomatic non-fatal PE, incidental PE and VTE-related deaths), fatal/non-fatal ATE (composite of MI, stroke or any ATE), and fatal/non-fatal visceral VTE event (*composite: primary efficacy composite endpoint event components, ATE events, and visceral VTE events*).
- Composite endpoint #4: Time to first occurrence of the composite of symptomatic lower extremity proximal DVT, symptomatic lower extremity distal DVT, symptomatic upper extremity DVT, symptomatic non-fatal PE, VTE-related deaths, and major bleeding event (*composite: symptomatic events and include major bleeding events for the ITT population and up-to-Day 180 observation period*).

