1. INTRODUCTION

This statistical analysis plan (SAP) specifies definitions of analysis populations, derived variables, and statistical methods for analysis of efficacy and safety for the Phase 3b study BAY59-7939/JNJ39039039STM4001. This SAP is based on the Clinical Protocol BAY59-7939/JNJ39039039STM4001 Amendment INT-4 finalized on February 16, 2018.

Titles, mock-ups and programming instructions for all statistical outputs (tables, figures, and listings) will be provided in a separate document entitled Data Presentation Specifications (DPS). This study SAP will be finalized prior to database lock.

This study SAP is also used for the Independent Data Monitoring Committee (IDMC) pre-specified safety reviews. For the IDMC however the definitions and imputation rules are defined based on the data cutoffs and accumulating data at the time of each DMC meetings.

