1.1. Study Objectives

Primary Objective

The primary efficacy objective is to demonstrate that rivaroxaban is superior to placebo for reducing the risk of the primary composite outcome as defined by objectively confirmed symptomatic lower extremity proximal DVT, asymptomatic lower extremity proximal DVT, symptomatic lower extremity distal DVT, symptomatic upper extremity DVT, symptomatic non-fatal PE, incidental PE, and VTE-related deaths in ambulatory adult subjects with various cancer types receiving systemic cancer therapy who are at high risk of developing a VTE.

Secondary Objectives

The key secondary efficacy objectives of this study are to compare the efficacy of rivaroxaban with placebo for reducing the risk of symptomatic VTE events and VTE related deaths and all-cause mortality in ambulatory adult subjects with various cancer types receiving systemic cancer therapy who are at high risk of developing a VTE.

Other secondary efficacy objectives include the evaluation of the individual components of the primary efficacy composite outcome variable, confirmed fatal/non-fatal arterial thromboembolism (ATE) events, confirmed fatal/non-fatal visceral VTE events, symptomatic lower extremity distal DVT, a composite of symptomatic lower extremity proximal DVT, asymptomatic lower extremity proximal DVT, symptomatic upper extremity DVT, symptomatic non-fatal PE, incidental PE, and all-cause mortality, and a composite of symptomatic lower extremity proximal DVT, symptomatic lower extremity distal DVT, symptomatic upper extremity DVT, symptomatic non-fatal PE, and VTE-related deaths.

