5.6.2. Analysis Methods

Analysis of the other secondary efficacy endpoints will follow the same approach as in the analysis of the primary efficacy endpoint analysis. These analyses will be based on the ‘Up-to-Day 180’ observation period for the ITT population with censoring as defined above (Section 2.6).

In addition to be above endpoints, the key secondary endpoints (time to symptomatic VTE events or VTE-related deaths, all-cause mortality) will also be analyzed based on the ‘Up-to-Day 180’ observation period for the ITT population.

The cumulative distribution function of the time to first occurrence of each of these endpoints will be estimated by the Kaplan-Meier method and tested using a log-rank test, stratified by tumor type. In addition, a Cox proportional hazard model with treatment and stratification factor as covariates will be fitted. A point estimate along with 2-sided 95% CI for the treatment effect of RRR (RRR=100 x [1-HR] %) will be provided.

The cumulative event rate derived from Kaplan-Meier estimate will also be displayed graphically to evaluate the timing of event occurrence and the consistency of the treatment effect over time. No multiplicity adjustment will be performed for the analysis of these endpoints.

Frequency summary (N, %) of the total number of deaths and the primary cause of death, total number of subjects with myocardial infarction (MI), stroke, and other arterial thrombosis (ATE) events will also be presented for the Up-to-Day 180 observation period.

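### The secondary endpoint named arterial thrombosis (ATE) counts primary intracranial bleeds as stroke, and no planned analysis isolates the thrombotic events

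*SAP*

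**What the plan says.** Section 1.1 lists among the other secondary objectives "confirmed fatal/non-fatal arterial thromboembolism (ATE) events", and the abbreviation list expands ATE as an arterial thrombosis event. Section 5.6 describes the outcome as "these will include the following events: occurrence of a stroke, MI or any arterial thrombosis event".

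Section 5.6.1 gives the operational definition. Stroke means ischemic infarction, with or without hemorrhagic conversion, or a primary hemorrhagic event. The list of the latter, and the definition, end with "intraparenchymal hemorrhage, subdural hematoma or epidural hematoma] or any other ATE recorded on eCRF". Composite endpoint #3 takes in the same component: "fatal/non-fatal ATE (composite of MI, stroke or any ATE), and fatal/non-fatal visceral VTE event".

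Section 5.6.2 analyses these endpoints in the ITT population over the Up-to-Day 180 period by Kaplan-Meier, stratified log-rank test and Cox model with RRR. It adds that "No multiplicity adjustment will be performed for the analysis of these endpoints". It also plans a frequency table of the "total number of subjects with myocardial infarction (MI), stroke, and other arterial thrombosis (ATE) events".

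Section 6.1.1 names the intracranial space as a critical site for ISTH major bleeding. Section 6.1.2.2 summarizes major bleeds by primary location, On-Treatment in the Safety population. Composite endpoint #4 combines symptomatic VTE and VTE-related death with major bleeding; its note reads "include major bleeding events for the ITT population and up-to-Day 180 observation period".

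**The concern.** Intraparenchymal hemorrhage and subdural and epidural hematoma are bleeds. Section 5.6.1 lists them separately from infarcts with hemorrhagic conversion, so borderline transformed infarcts are not the issue.

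One subdural hematoma on study drug can count as a primary safety event, as an efficacy event under the heading of arterial thrombosis, and as an event in composite #3. An anticoagulant may reduce arterial thrombosis and increase intracranial bleeding. The pooled RRR then measures neither effect, and a reader who takes the endpoint's name at face value will misread it. An ischemic-only result produced after unblinding to resolve the ambiguity would be post hoc.

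**Working it through.** **What each planned output can show**

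| Output | Population / period | Separates thrombotic ATE from bleeds? |
|---|---|---|
| ATE time-to-event (5.6.1, 5.6.2) | ITT, Up-to-Day 180 | No, pooled |
| Composite #3 | ITT, Up-to-Day 180 | No, inherits the definition |
| Counts of MI, stroke, other ATE (5.6.2) | Up-to-Day 180 | Partly: MI and other ATE are separate, but no stroke subtype is stated |
| Composite #4 | ITT, Up-to-Day 180 | No, major bleeding pooled with symptomatic VTE |
| Major bleeding by location (6.1.2.2) | Safety, On-Treatment | Bleeds only, different population and period |

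**Inputs for an illustration.** From the SAP: about 800 subjects (sections 1.2 and 1.4), so 400 per arm; primary event rates 14.5% and 6.0% (section 1.4). Assumed, because the SAP gives no such rates: placebo thrombotic ATE 2% (range 1% to 3%), thrombotic HR 0.70, hemorrhage 0.25% to 1.0%, independence of the event types.

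**Formulas**
- Thrombotic risk on rivaroxaban: 1 − (1 − p_pl)^0.70
- Pooled risk per arm: p = 1 − (1 − p_thr)(1 − p_hem)
- HR = ln(1 − p_riv) / ln(1 − p_pl)
- SE(ln HR) = √(1/e1 + 1/e2), with e the events per arm

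**Base case.** Thrombotic risk on rivaroxaban is 1 − 0.98^0.70 = 1.404%. On the −ln(1 − p) scale:
- Thrombotic ATE: placebo 0.02020, rivaroxaban 0.01414
- Hemorrhage of 0.25%, 0.5%, 1.0%: 0.00250, 0.00501, 0.01005

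*Equal hemorrhage in both arms*
- 0.25%: (0.01414 + 0.00250)/(0.02020 + 0.00250) = 0.73
- 0.5%: (0.01414 + 0.00501)/(0.02020 + 0.00501) = 0.76
- 1.0%: (0.01414 + 0.01005)/(0.02020 + 0.01005) = 0.80

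*Placebo hemorrhage 0.25%, rivaroxaban varying*

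| Placebo thrombotic ATE | Riv. hemorrhage 0.25% | 0.5% | 1.0% | Riv. hemorrhage at which HR = 1.00 |
|---|---|---|---|---|
| 1% | 0.76 | 0.96 | 1.36 | 0.55% (2.2 of 400) |
| 2% | 0.73 | 0.84 | 1.07 | 0.85% (3.4 of 400) |
| 3% | 0.72 | 0.80 | 0.95 | 1.16% (4.6 of 400) |

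Break-even in the base case is 1 − (0.98 × 0.9975)/(1 − 0.01404) = 0.85%. That is 3.4 subjects against 0.0025 × 400 = 1.0 on placebo, a difference of about 2.4. If the thrombotic HR is 1.00, the base-case row becomes 1.00, 1.11 and 1.33.

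**Precision**
- Pooled HR 1.07: 9.0 events on placebo and 9.6 on rivaroxaban, SE = √(1/9.0 + 1/9.6) = 0.46, 95% CI 0.43 to 2.65.
- Ischemic-only HR 0.70: 8.0 and 5.6 events, SE = √(1/8.0 + 1/5.6) = 0.55, 95% CI 0.24 to 2.06.

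**Composite #3** (VTE 14.5% vs 6.0%, i.e. 0.15665 and 0.06188 on the same scale; visceral VTE ignored)
- Without hemorrhage: (0.06188 + 0.01414)/(0.15665 + 0.02020) = 0.430
- With placebo hemorrhage 0.25% and rivaroxaban 0.25%, 0.5%, 1.0%: 0.438, 0.452, 0.480
- Largest shift in the scenarios examined: 0.413 to 0.467 (thrombotic ATE 1%)

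**The case against.** The definition is explicit and looks deliberate. Section 5.6 already lists stroke without restriction, and the amendment history records that the ATE definition was clarified. All-stroke is a legitimate component, and the protocol or CEC Charter, neither at hand, may fix it. MI and other ATE are counted separately, so only the stroke line is mixed, and the bleeding-location table should reveal on-treatment intracranial bleeds. The rates above are assumed. With equal hemorrhage the HR moves only from 0.70 to 0.73–0.80, and the intervals are too wide for either version to support a conclusion. The endpoints sit outside the hierarchy, and if rivaroxaban raises intracranial bleeding the pooling works against rivaroxaban. A label and a subtype row might be enough.

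Most of this stands and limits the size of the point. It does not remove it. An all-stroke endpoint may be kept, but its name should say so. The stroke counts are not stated by subtype, and the location table covers a different population and period. Table layout belongs to the separate Data Presentation Specifications, but section 1 says that this SAP "specifies definitions of analysis populations, derived variables, and statistical methods for analysis of efficacy and safety". An ischemic-only time-to-event analysis is a derived variable and a method, so it belongs here.

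**Conclusion.** The point holds. The name and the definition disagree, and no output specified in the SAP isolates thrombotic ATE in ITT/Up-to-Day 180. Under the assumed base case, an excess of about 2.4 bleeding subjects in 400 on rivaroxaban is enough to bring a thrombotic HR of 0.70 to a pooled 1.00; with equal bleeding rates the effect is a modest dilution. Composite #3 changes by about 0.05 at most.

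What is affected is the meaning of the estimate, not a significance decision. The primary, key secondary and primary safety conclusions are untouched. All ATE and hemorrhage rates, the thrombotic HR and the independence of event types are assumptions. The change is worth making because it is cheap, but its importance is limited.

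**What to change.** Before unblinding:

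1. In 5.6.1 and 5.6.2, add an ITT/Up-to-Day 180 analysis of ATE, and of composite #3, with stroke restricted to ischemic infarction with or without hemorrhagic conversion. Base any statement about arterial thrombosis on it.
2. If the present definition is kept, for example because the protocol or CEC Charter fixes it, label it as MI, any stroke (ischemic or primary hemorrhagic) or other ATE in sections 1.1, 5.6 and 5.6.1, including composite #3.
3. In the 5.6.2 frequency summary, split stroke into ischemic and primary hemorrhagic.

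The cost is label wording, one derivation, two analyses and one table split; the existing endpoint need not be redefined. The ischemic-only version has somewhat fewer events: 8.0 + 5.6 = 13.6 in the base case, against about 15.6 to 18.5 pooled when placebo hemorrhage is 0.25%. The change also needs stroke subtype to be recorded on the eCRF or by the CEC. The definition implies this, but the SAP does not state it, so it should be confirmed first.
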